4.1.2 Maintenance Phase

4.1.2.1 Maintenance Phase Overview

Participants who have not progressed per RECIST v1.1 at the end of the induction phase and who meet maintenance phase eligibility criteria will continue into the maintenance phase of the trial and be treated with AZD2811 + durvalumab as maintenance therapy (Table 9) until radiological progressive disease (PD), unless there is unacceptable toxicity, withdrawal of consent, or another discontinuation criterion is met (Section 7.1).

Table 9 Study Intervention During the Maintenance Phase

Day and order of administration in each cycle	Agent and dose	Route	Duration	Observation time	Schedule
CCI	AZD2811 CCI ^a	IV	CCI		
	Durvalumab CCI	IV			
	Filgrastim 0.5 MU (5 µg)/kg/day SC from CCI (DAILY until at least CCI of each cycle AND the ANC has recovered to $\geq 1.5 \times 10^9/L$) or Neulasta (pegfilgrastim) 6 mg dose SC on CCI only	SC			

^a Dose reduction levels are provided in Section 6.6.1

^b Participants are treated until PD unless there is unacceptable toxicity, withdrawal of consent, or another discontinuation criterion is met

ANC = absolute neutrophil count; G-CSF = granulocyte colony stimulating factor; IV = intravenous; MU = million units; N/A = not applicable; PD = progressive disease; CCI [REDACTED]; SC = subcutaneously.

Hematopoietic growth factors (short-acting granulocyte colony stimulating factor [G-CSF] [filgrastim] or long-acting G-CSF [pegfilgrastim]), must be administered as primary prophylaxis on/from CCI [REDACTED] of every maintenance cycle to limit the duration of neutropenia, and to minimize the risk of neutropenic fever and infections. If short-acting G-CSF (filgrastim) is used, administer DAILY until at least CCI [REDACTED] of each cycle AND the ANC has recovered to $\geq 1.5 \times 10^9/L$. Long-acting G-CSF should be administered once only per cycle on CCI [REDACTED]

For all participants who are treated through progression with durvalumab monotherapy, the investigator should ensure participants do not have any significant, unacceptable, or irreversible toxicities that indicate continuing treatment would not further benefit the participant. AZD2811 must not be administered through progression.

4.1.2.2 Safety Run-In

CCI [REDACTED]

[REDACTED]

[REDACTED]

[REDACTED]

Nevertheless, because the amount of safety data on this combination is still expected to be from a limited number (≤ 6) of participants when this trial starts, a safety run-in will be conducted, in which six participants will be followed for (at least) 1 cycle to assess safety of the AZD2811 + durvalumab combination. The study procedures and safety assessments undertaken for the safety run-in period will be as per the Schedule of Activities (Table 1). The safety run-in will comprise participants as defined in the inclusion and exclusion criteria (Section 5.1 and 5.2) to provide the earliest opportunity to assess tolerability of the combination in those six participants.

After administration of the first dose of AZD2811 + durvalumab to the first participant, at least 24 hours must be allowed before administration to the second participant in case of unexpected acute toxicity.

A participant will be evaluable for the safety run-in (described as dose-limiting toxicity [DLT]) safety assessment if they have received at least 75% of the scheduled AZD2811 and durvalumab doses, or had a DLT. Non-evaluable participants will be replaced. After the completion of \geq CCI [REDACTED] (≥ 1 cycle) dosing in the first 6 evaluable maintenance therapy

participants, all available safety data (including, but not limited to, DLTs, adverse events of special interest (AESIs), laboratory safety assessments, and clinical examinations) will be assessed to judge if the combination is safe and tolerable. This assessment, and subsequent decision to continue dosing further participants, will be undertaken by the SRC. The SRC membership is described in Appendix A 5. The role and responsibilities of SRC members, as well as the purpose and timing of the SRC meetings, are described in the SRC Charter.

The purpose of the safety run-in is to confirm the dose of AZD2811 and durvalumab in the combination setting. Treatment of new participants entering the maintenance phase with AZD2811 + durvalumab will be paused (after ~six participants) while the SRC convenes to assess the safety data at the end of the safety run-in phase if a DLT event is observed in any of the first ~six participants. In absence of clarity on the feasibility of the proposed combination maintenance therapy, transition of participants beyond the approximately six participants to the maintenance therapy, can be paused until confirmation of feasibility. In the event of a pause, new participants entering the maintenance phase would receive treatment with durvalumab monotherapy, as this represents standard of care treatment for ES-SCLC patients. Following a pause, if dosing with AZD2811 resumes, participants receiving durvalumab monotherapy will be allowed to start dosing with AZD2811 if maintenance phase eligibility criteria are met. In the absence of a DLT event in any of the first ~six participants, treatment with AZD2811 + durvalumab into the maintenance phase will not be paused while the SRC convenes. Participants from the safety run-in phase will contribute to the required treatment assignment as described in Section 9.3.

4.1.2.2.1 Results of the Safety Run-In

Treatment in the maintenance phase of the trial began in June 2021 and the SRC completed an initial assessment of the safety run-in cohort in September 2021. While no DLTs were experienced by the first six participants, one participant experienced an SAE of neutropenic sepsis with a fatal outcome and one participant experienced an SAE of febrile neutropenia with a fatal outcome during the second cycle of AZD2811 treatment (ie, CCI [REDACTED] Both SAEs were attributed to AZD2811 treatment by the investigators. Additional information about these events and the identified risk of sepsis has been added to the Investigator's Brochure.

Treatment with AZD2811, of new participants entering the maintenance phase, was put on hold while additional data analyses were conducted, and the following protocol amendments were proposed to ensure the safety of current and future participants:

- Maximum AZD2811 dose permitted will be CCI [REDACTED]; maintenance phase eligibility criteria must be confirmed prior to dosing the first cycle of AZD2811
- AZD2811 must not be administered if there is any suspicion of disease progression. Every effort should be made to schedule tumour evaluation scans within 1 week prior

to dosing with AZD2811; scan results **MUST be reviewed** prior to dosing to confirm the absence of disease progression.

- AZD2811 must not be administered if there is any suspicion of infection; consider (prophylactic) antibiotics for participants experiencing Grade 4 ANC or at a high risk of infection. If infection is suspected, work up should be performed to identify whether there is an infection.
- AZD2811 dose will be reduced if a patient experiences Grade 4 ANC, irrespective of time to recovery
- An additional safety visit on Day 12 of [CC1] has been introduced to identify low ANC earlier in the cycle (from Phase I experience, the nadir is expected between 10 to 15 days after AZD2811 dosing).

After implementation of the above recommendations in CSP v8.0, an additional safety run-in cohort will be assessed by the SRC according to Section 4.1.2.2.

4.1.3 DLT Criteria

A DLT will be considered for any toxicity observed unless unequivocally due to underlying malignancy or an extraneous cause.

The DLT evaluation period is defined as the first [CC1] from the start of AZD2811 + durvalumab administration. Toxicity will be graded according to the National Cancer Institute Common Terminology Criteria for Adverse Events (NCI CTCAE) v5.0. The definition of an evaluable participant is found in Section 4.1.4. The following toxicities constitute a DLT:

- Grade 4 neutropenia, or febrile neutropenia.
- Grade 4 anemia.
- Grade 4 thrombocytopenia, or Grade 3 thrombocytopenia associated with bleeding.
- Concurrent Grade ≥ 3 total bilirubin (TBL), hepatic transaminase (alanine aminotransferase [ALT] or aspartate aminotransferase [AST]) and alkaline phosphatase lasting > 48 hours, or any change in liver function test results consistent with Hy's Law (HL; see Appendix E).
- Any \geq Grade 3 non-hematologic AE with the exception of:
 - Grade 3 nausea, vomiting, stomatitis, and/or diarrhea that is controlled within 4 days with standard supportive care. Use of prophylactic mouthwash to prevent stomatitis is allowed and should be used according to local site practices.
 - Grade 3 fatigue and/or decreased appetite (anorexia) that resolves within 5 days

- Grade 3 elevations in ALT/AST that return to initial eligibility criteria within 7 days of study drug interruption.
- Inability to receive \geq 75% of all doses in Cycle 1 of maintenance due to treatment-related toxicity.
- Non-hematologic toxicity of \geq Grade 3 (at any time during treatment) that, in the judgment of the investigators and the Study Physician, is dose limiting.

4.1.4 Definition of DLT-Evaluable Participants

An evaluable participant for the purpose of the safety run-in decision is defined as a participant who has received AZD2811 + durvalumab and either:

- Has completed the minimum safety evaluation requirements of the study (ie, safety assessments in the SoA [Table 1] up to and including ^{CC1} in Cycle 1 maintenance of AZD2811 + durvalumab) and received at least 75% of the scheduled AZD2811 and durvalumab doses, or
- Has experienced a DLT in Cycle 1 of maintenance therapy

4.1.5 Study Conduct Mitigation During Study Disruptions Due to Cases of Civil Crisis, Natural Disaster, or Public Health Crisis

The guidance given below supersedes instructions provided elsewhere in this CSP and should be implemented only during cases of civil crisis, natural disaster, or public health crisis (e.g., during quarantines and resulting site closures, regional travel restrictions, and considerations if site personnel or study participants become infected with SARS-CoV-2 or similar pandemic infection), which would prevent the conduct of study-related activities at study sites, thereby compromising the study site staff or the participant's ability to conduct the study. The investigator or designee should contact the study Sponsor to discuss whether the mitigation plans below should be implemented.

To ensure continuity of the clinical study during a civil crisis, natural disaster, or public health crisis, changes may be implemented to ensure the safety of study participants, maintain compliance with Good Clinical Practice (GCP), and minimize risks to study integrity.

Where allowable by local health authorities, ethics committees, healthcare provider guidelines (e.g., hospital policies) or local government, these changes may include the following options:

- Rescreening: Additional rescreening for screen failure and to confirm eligibility to participate in the clinical study can be performed in previously screened participants. The investigator should confirm this with the designated Study Physician.

- Home or Remote visit: Performed by a site qualified Health Care Professional (HCP) or HCP provided by a third-party vendor.
- Telemedicine visit: Remote contact with the participants using telecommunications technology, including phone calls, virtual or video visits, and mobile health devices.

For further details on study conduct during civil crisis, natural disaster, or public health crisis, refer to Appendix H.

4.2 Scientific Rationale for Study Design

4.2.1 Rationale for CCI of Induction Therapy

The use of platinum-based chemotherapy in combination with etoposide has been SOC for SCLC for over 40 years. Current investigations are now adding immunotherapeutics to chemotherapeutics to broaden antitumor responses. In March 2020, the FDA approved the use of durvalumab in combination with 4 cycles of etoposide and either carboplatin or cisplatin, and durvalumab in maintenance therapy, as first-line treatment of patients with ES-SCLC. Efficacy of this combination in patients with previously untreated ES-SCLC was investigated in CASPIAN, a randomized, multicenter, active-controlled, open-label trial. The evaluation was based on the comparison of patients randomized to durvalumab plus chemotherapy, followed by durvalumab maintenance therapy, versus chemotherapy alone. Median OS was 13.0 months in the durvalumab plus chemotherapy arm and shown to be superior compared to 10.3 months in the chemotherapy alone arm having 6 cycles of chemotherapy (Paz-Ares et al, 2019). As such, 4 cycles of chemotherapy, when combined with durvalumab and followed by durvalumab maintenance therapy, appears to be superior to 6 cycles of chemotherapy alone.

The durvalumab + platinum-based induction chemotherapy induction regimen will be administered for CCI followed, in participants who do not have PD at the end of induction, by AZD2811 + durvalumab combination maintenance therapy CCI until disease progression or unacceptable toxicity.

4.2.2 Rationale for AZD2811 and Durvalumab Maintenance Therapy

The interest of durvalumab in 1L ES-SCLC has been established with giving durvalumab in combination with platinum-etoposide and in maintenance therapy in terms of landmark 12-month PFS and OS, as demonstrated in the CASPIAN study. AZD2811 has demonstrated activity in relapsing SCLC in an expansion cohort of the AZD2811 first in human trial (NCT02579226). Twenty-one patients who had failed SOC and up to 3 lines of therapy were treated with CCI AZD2811 CCI Clinical benefit (defined as CR, PR, or SD \geq 8 weeks) was demonstrated in > 50% of the participants, and median OS in this patient population was 9.95 months (data on record).

Nonclinical and clinical studies have indicated that blockade of immune checkpoints (PD-1/PD-L1) can have a positive effect on disease control in SCLC patients, as described in Section 2.2.2.

The therapy safety profile of durvalumab and AZD2811 suggest that both drugs can be combined in the absence of overlapping toxicities. Both drugs have demonstrated clinical benefit in SCLC, and there is clear medical need to improve the efficacy of the current therapy in ES-SCLC. Therefore, investigating the efficacy of the combination of durvalumab with AZD2811 is a rational next step.

4.3 Justification for Dose

4.3.1 Rationale for Dose of Platinum-based Chemotherapy

The doses of platinum-based chemotherapy to be used in this study are the approved doses for this indication.

4.3.2 Rationale for Dose of AZD2811

The initial proposed AZD2811 dosing schedule, [CC1] on [CC1] with mandatory G-CSF on [CC1] is based on data from a Phase I dose escalation and expansion study: D6130C00001/NCT02579226.

In Part A of study D6130C00001, several AZD2811 dosing schedules were evaluated. Doses ranging from [CC1] AZD2811 were administered IV on [CC1] of every [CC1] cycle. After switching to single day treatment per cycle, the cycle length was shortened to cycles of [CC1] duration to decrease time between infusions and increase the dose intensity, evaluating doses ranging from [CC1] to [CC1] mg infused on Day 1. On [CC1] G-CSF was introduced and mandated to ensure recovery of neutrophils before Day 1 of the next cycle. AZD2811 [CC1] on [CC1] with mandatory G-CSF on [CC1] was declared the maximum tolerated dose (MTD) and recommended Phase II dose. Activity and safety of this regimen was further supported by data from a dose expansion phase: D6130C00001 Part B.

Exposure-response analysis of data from D6130C00001 indicates that an AZD2811 dose above [CC1] would result in unfavorable rates of severe (Grade 4) neutropenia, further supporting the proposed AZD2811 dosing schedule. Therefore, G-CSF is mandated for this dose and schedule. Further details of the results from Study D6130C00001 are available in the AZD2811 IB.

Subsequent to the review of the safety run-in cohort of the current study (see Section 4.1.2.2.1), the starting dose of AZD2811, in combination with durvalumab in the maintenance phase, has been reduced to a maximum of [CC1] on [CC1] with mandatory G-CSF on/from [CC1] to decrease the rate of Grade 4 neutropenia.

Dose reductions for AZD2811 are detailed in Section 6.6.1.

4.3.3 Rationale for Dose of Durvalumab

The dosing schedule proposed during the induction phase is aligned with the standard fixed dosing of [CC1] durvalumab for [CC1] of [CC1] duration followed by durvalumab maintenance therapy, which is supported by efficacy and safety as well as tolerability data from the CASPIAN clinical trial.

The durvalumab dosing regimen during the maintenance phase was aligned to the AZD2811 [CC1] regimen with standard fixed dosing of [CC1] durvalumab [CC1]. The proposed durvalumab regimen is dose-matched (ie, equivalent dose per week) to the regimen tested in the CASPIAN clinical trial maintenance setting – durvalumab [CC1] every [CC1] dosing – and further supported by preliminary safety as well as tolerability data from the HUDSON (NCT03334617) clinical trial.

4.4 End of Study Definition

The end of the study is defined as the date of the last scheduled procedure shown in the SoA for the last treated participant in the study, globally.

The study may be terminated at individual centers if the study procedures are not being performed according to GCP or if the site is unable to recruit sufficient numbers of participants into the study.

The AstraZeneca Study Team may also terminate the study prematurely if concerns for safety arise within this study or in any other study with any agent used in this study.

As a result of the early termination of this study, the data cut-off (DCO) for the final analysis is planned for 18 June 2022, approximately 5 months after last participant first dose. Main data collection will stop at that point. Data analysis will be performed and a clinical report will be written based on this dataset. Serious AEs will be collected per Section 8.3.2.

Participants who are receiving treatment at the time of DCO can either choose to discontinue from the study or, when the investigator believes participants are gaining clinical benefit, may continue to receive study treatment, following discussion with, and approval from, the AstraZeneca Study Team.

Patients' treatment may be continued:

- Within the current study, or
- Within a rollover or safety extension study, if available, or

- Within a drug supply program (commercial supply or other compassionate use program), if applicable

In case of treatment continuation within the current study:

- Assessments will revert to standard of care at each site
- There will be no further data collection, except SAE reporting. The Clinical Study Database will be closed
- Paper form process will be used for SAE reporting. All SAEs, overdoses and pregnancies would be reported until 30 days after last dose
- Investigational product will be supplied to sites manually outside of the IXRS system. Drug dispensation and reconciliation will be handled by site at each patient's visit
- Study will remain open until last patient completes treatment. Last Subject Last Visit will be defined as the last patient's treatment discontinuation

In case a rollover or safety extension study is available for patients remaining in this study after analysis is finalized, they may be transferred to one of these studies:

- A rollover or safety extension study would have to be fully approved by Regulatory and Ethics bodies applicable for the patient's site
- The new study would ensure proper treatment continuation with visit assessments per its own protocol
- Visit assessments would cover the minimum needed for safety oversight. May also cover assessments required for long term use analysis
- Any patient that was to move to such a study would need to be reconsented beforehand

If study drug is approved in a given market for use in the disease under study, patients may be discontinued and switched to marketed product. Drug supply options will vary depending on the specific country and would be proposed to patients if they are considered the best way to continue treatment by both AZ and the investigator.

See Appendix A 6 for guidelines for the dissemination of study results.

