6.1.3 Duration of Treatment and Criteria for Treatment After Initial Assessment of PD

Maintenance treatment will start on CCI [REDACTED]. Participants who do not have any evidence of radiological disease progression during the induction phase (CCI [REDACTED] of EP-durvalumab)

and who meet maintenance phase eligibility criteria (see Section 5.3) will continue into the maintenance phase of the trial.

In the rare instances when the RECIST v1.1-defined radiological findings are considered equivocal by the investigator or there is doubt whether or not there is evidence of objective progression (e.g., technical issues, including image artifacts), the participant may not move into the maintenance phase of the study without prior discussion with the Sponsor.

Upon initial assessment of PD, treatment with AZD2811 must be discontinued. Treatment with durvalumab may be continued until radiological PD is confirmed by the subsequent scan, unless there is unacceptable toxicity, withdrawal of consent, or another discontinuation criterion is met. Participants with rapid tumor progression or with symptomatic progression that requires urgent medical intervention (e.g., central nervous system [CNS] metastasis, respiratory failure due to tumor compression, or spinal cord compression) will not be eligible to continue study treatment. All efforts should be put in place to perform a disease assessment to document this disease progression.

Post final data cut-off

Participants who are receiving treatment at the time of DCO can either choose to discontinue from the study or, when the investigator believes participants are gaining clinical benefit, may continue to receive study treatment, following discussion with, and approval from, the AstraZeneca Study Team. For participants continuing to receive study treatment following the final DCO and database closure assessments will revert to standard of care.

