8.2.5 Early Participant Review for Safety

Participants will be evaluated 15 days after the first dose of each cycle of chemotherapy and on Days 8 and 15 of each maintenance cycle to ensure early identification and management of toxicities by the investigator. Participants will also be evaluated on Day 12 of Cycles [CC1] (the first [C] cycles of AZD2811 treatment).

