For all toxicities leading to a dose hold, discontinue AZD2811 treatment if the toxicity does not resolve to NCI CTCAE \leq Grade 1 or baseline after 14 days (ie, by Day 35 of a cycle), with exceptions noted below.	
Non-Hematologic Toxicity	
Grade 3 non-hematologic toxicity lasts > 4 but ≤ 7 days and resolves to \leq Grade 1 or baseline	
 At first occurrence, consider restarting at the same dose If second occurrence (≤ 7 days) Grade 3, reduce to dose level -1 If third time: Reduce to dose level -2 and discuss risk-benefit analysis with Study Physician
Toxicity remains Grade 3 > 7 days (despite supportive therapy)	
 At first occurrence, reduce one dose level If second occurrence, reduce to dose level -2 and discuss risk-benefit analysis with Study Physician
Grade 4 non-hematologic toxicity lasts > 4 but ≤ 7 days and resolves to \leq Grade 1 or baseline	
 At first occurrence, reduce to dose level -1 If second time: Discuss with Study Physician whether risk-benefit analysis supports continuation
Grade 4 non-hematologic toxicity lasts > 7 days	Discuss with Study Physician whether risk-benefit analysis supports continuation
Grade 3 or 4 non-hematologic toxicity that does not resolve to \leq Grade 1 or baseline within 14 days	Discontinue study treatment unless approved by the Study Physician to continue
Sepsis, or any other Grade 3 or 4 non-hematological toxicity, not expected to be manageable/reversible with dose reduction	Discontinue study drug
Hematologic Toxicity	
Participants can only be dosed with AZD2811 on Day 1 of any Cycle if the ANC is $\geq 1.5 \times 10^9/L$ and the platelet count is $\geq 75 \times 10^9/L$.	
Grade 0-3 (except as noted below)	Maintain dose
Grade 2-3 ANC; or Grade 2-3 thrombocytopenia without bleeding or requirement for platelet transfusion	
 Hold until recovery and then maintain dose
Grade 3 thrombocytopenia with bleeding or requiring a platelet transfusion; or Grade 4 ANC	
 First occurrence: Hold until recovery and then reduce to dose level -1 Second occurrence: Dose reduce to level -2 and discuss with Study Physician whether risk-benefit analysis supports continuation

Table 21 Dose Modification for Non-skin Toxicity

NCI CTCAE v5.0 Toxicity Grade	Action

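### Sections 4.4 and 6.1.3 return assessments to site standard of care after the cut-off with no exception for AZD2811, which conflicts with the protocol's per-cycle AZD2811 monitoring

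*Protocol*

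**What the plan says.** Section 4.4 (End of Study Definition) sets the final cut-off at 18 June 2022. Participants on treatment then, whom the investigator believes to be benefiting, "may continue to receive study treatment, following discussion with, and approval from, the AstraZeneca Study Team". One route is continuation within this study, for which "Assessments will revert to standard of care at each site" and "There will be no further data collection, except SAE reporting"; the same list also requires overdoses and pregnancies to be reported, until 30 days after the last dose. Section 6.1.3 repeats the rule: "For participants continuing to receive study treatment following the final DCO and database closure assessments will revert to standard of care".

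Other sections carry no end date tied to the cut-off:

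- Section 8.2.5: participants are evaluated "on Days 8 and 15 of each maintenance cycle to ensure early identification and management of toxicities by the investigator".
- Section 6.2.4: blood counts on Days 8, 12 (Cycles 5 and 6) and/or 15 as a minimum.
- Sections 4.1 and 8.1: scans on a fixed schedule, with results reviewed before AZD2811 is given.
- Section 8.5.1, Table 21: "Participants can only be dosed with AZD2811 on Day 1 of any Cycle if the ANC is" at least 1.5 × 10⁹/L and platelets are at least 75 × 10⁹/L.
- Section 8: adherence to the Schedule of Activities is required, with waivers only in a civil, natural or public health crisis.

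**The concern.** The post-cut-off rule speaks of study treatment in general, and in the maintenance phase that is AZD2811 plus durvalumab with G-CSF (Table 11). For durvalumab, standard of care at a site has a meaning: Section 4.1.2.2 calls durvalumab monotherapy standard of care in this disease. For AZD2811 it has none. Section 6.5.3.1 describes the drug as investigational, and Table 6 says nothing comparable is known.

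The stake is patient safety, not the analysis. Section 4.1.2.2.1 reports two fatal SAEs that investigators attributed to AZD2811: one of neutropenic sepsis, and "one participant experienced an SAE of febrile neutropenia with a fatal outcome during the second cycle of AZD2811 treatment". The same section expects the neutrophil nadir 10 to 15 days after dosing. A site that followed Section 4.4 literally would have no stated duty to look at counts in that interval. A missed count would not appear in the data still collected.

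**Working it through.** No figure in the plan needs reproducing. The check sets the passages side by side and adds some arithmetic on dates and counts.

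**1. Is continued AZD2811 within the rule?** Section 4.1 bars new AZD2811 starts after 14 December 2021. Section 9 says enrolled patients could go on receiving study treatment. Section 4.4 provides for investigational product to be supplied after the cut-off, and SAP Section 2.1 defines investigational product as AZD2811 and durvalumab. SAP Section 3.2.1.5 provides for patients dosed with AZD2811 after 28 September 2021. No passage excludes continuation, and none says that anyone was still on the drug.

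**2. What does the rule displace?**

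| Requirement | Scope as written | Effect of Sections 4.4 and 6.1.3 |
|---|---|---|
| Day 8 and 15 reviews (8.2.5) | Each maintenance cycle | Conflict: an assessment, now at site standard of care |
| Minimum count days (6.2.4) | Each AZD2811 cycle | Conflict, for the same reason |
| Scan schedule (4.1, 8.1) | Until confirmed progression | Conflict: the schedule behind the pre-dose review lapses |
| Review of scan results before AZD2811 (4.1, 8.1) | Before dosing | Not withdrawn, but which scan is unstated |
| ANC and platelet thresholds (8.2.4, Table 21) | Day 1 of any cycle | Not withdrawn, but needs a count; persistence unstated |
| Infection hold, Grade 4 ANC rule (8.5.1, Table 21) | Dosing rules | Not withdrawn; persistence unstated |
| Day 12 visit (Table 3, 8.2.5) | First AZD2811 cycles only | Should be over by the cut-off (step 3) |

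**3. Would the Day 12 visits be over?** Section 8.5.1 equates a 14-day delay with Day 35, which implies a cycle of 35 − 14 = 21 days. The cycle length itself is redacted, so this is an inference. Day 12 of the second AZD2811 cycle then falls on day 21 + 12 = 33, or on day 35 + 12 = 47 after a first cycle of maximum length. Two maximum-length cycles take 2 × 35 = 70 days. From 14 December 2021, the last possible start, to 18 June 2022 is 186 days (26.6 weeks). Unless an interruption exceeded the permitted delay, every mandatory Day 12 visit was finished long before the cut-off.

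**4. Which scheduled visits cover the nadir?** Section 8.5.1 makes Day 1 the dosing day. Day 8 is therefore 7 days after dosing and Day 15 is 14 days after. On the inferred 21-day cycle the next Day 1 is 21 days after. Once the Day 12 visits are over, Day 15 is the only nominal visit inside the expected 10 to 15 days. A Day 1 count comes 21 − 15 = 6 days after that interval ends.

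**5. How many people?** Section 9.4 gives 9 patients who received the combination. Two had fatal events, leaving at most 9 − 2 = 7. The number still on AZD2811 at the cut-off is not given, so the range is 0 to 7.

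**6. Does the protocol handle similar cases differently?** Section 7.1 allows Day 1-only visits, but for durvalumab monotherapy. Section 4.4 gives the rollover route a minimum set of visits for safety oversight. Appendix H 10 interrupts study intervention in a crisis when safety assessments cannot be done. In-study continuation has no equivalent statement.

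**The case against.** The best defence is that Section 4.4 speaks of assessments and leaves dosing rules alone. A reader might infer that the dosing preconditions are waived; the documents do not support that. Table 21, the infection hold, the stop at initial progression and the pre-dose scan review all govern administration, and no passage withdraws them. A site cannot satisfy Table 21 without a pre-dose count. Where short-acting G-CSF is used, it continues until neutrophils recover, which also calls for counts within the cycle.

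A reader might also infer that the monitoring added after the deaths is removed. That is not supported either. The added visit was Day 12, already complete by step 3. The Day 8 and 15 reviews are not among the measures listed in Section 4.1.2.2.1. Of the added monitoring, only scan timing relative to dosing could lapse, and the protocol asks for that as a best effort.

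Sections 6.2.4 and 8.2.5 do not themselves make dosing conditional, and Section 6.2.4 says and/or. Each continuation needs sponsor approval. The rule does not reach a rollover study, which would follow its own protocol.

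All of this stands and narrows the point. It does not remove it. The approval carries no stated monitoring condition, Section 8.2.5 applies to each maintenance cycle without limit, and no passage says which text governs after the cut-off.

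**Conclusion.** The concern holds in a limited form. For AZD2811 continued within this study after the cut-off, Sections 4.4 and 6.1.3 conflict with the Day 8 and 15 reviews, the minimum count days and the scan schedule. They also leave the standing of the Table 21 preconditions unstated.

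It affects 0 to 7 people, possibly none. The upper limit assumes that the two fatal events were in different participants and that both are counted among the 9. The Day 12 conclusion assumes the inferred 21-day cycle and no interruption beyond 14 days.

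It would be tempting to size the problem as 2 of 9, or 22%. That is the proportion with a fatal event before this rule applied, so it says nothing about the rule's effect and should not be used. No planned analysis changes. The reason to act is that the gap concerns monitoring around the nadir for a drug with two attributed fatal neutropenic events.

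**What to change.** Before the cut-off, reconcile Sections 4.4 and 6.1.3 with Sections 6.2.4, 8.1, 8.2.4, 8.2.5 and Table 21 by protocol clarification or site letter. State separately for AZD2811 and durvalumab which assessments and dosing preconditions stay binding for in-study continuation, even though they are no longer entered in the eCRF. If no participant will continue AZD2811, one sentence saying so closes the point. What the requirements should be is for the sponsor's physicians to set.

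The cost is one short document, with no added data collection and no change to the SAP or its outputs.
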